6. STUDY OBJECTIVES

Primary Objective

- To characterize the pulmonary safety, as assessed by spirometry (forced expiratory volume in 1 second [FEV1], forced vital capacity [FVC], and FEV1/ FVC ratio), over a 12-month period within the CVT-301-treated patients.

Secondary Objectives

- To characterize the pulmonary safety, as assessed by spirometry (FEV1, FVC, and FEV1/FVC ratio), over a 12-month period in the observational ('standard of care') cohort.
- To estimate the difference between the CVT-301-patients and the observational cohort on measures of pulmonary safety.
- To characterize the effects of CVT-301 on safety over a 12-month period: safety will be assessed by AE reports, physical examination, standard and orthostatic vital signs (BP, HR, and RR), clinical laboratory tests, 12-lead ECGs, QUIP, the Epworth Sleepiness Scale, and the C-SSRS.
- To evaluate the effect of CVT-301 on mean change from baseline in the UPDRS Part 4 measures of motor fluctuations (dyskinesias [Q32-35] and wearing off [Q36-39]) measured pre-dose at 6 and 12 months after the initiation of CVT-301 treatment.
- To characterize the occurrence and severity of examiner-rated dyskinesia following treatment of patients experiencing an OFF episode in the clinic over a 12-month period.
- To describe the effects of CVT-301 on DLco over a 12-month period.

Exploratory Efficacy Objectives

- Change from pre-dose in UPDRS Part 3 motor score at 10, 20, 30, and 60 minutes following treatment of patients experiencing an OFF episode.
- Time curves of the UPDRS response at 10, 20, 30 and 60 minutes will be evaluated descriptively

- Change from pre-dose in UPDRS Part 3 motor score at 10 to 60 minutes following treatment of patients experiencing an OFF episode.
- Proportion of patients with a ≥ 3 , ≥ 6 , and ≥ 11 -point reduction in the UPDRS Part 3 motor score from pre-dose to post-dose, at 10 to 60 minutes.
- Proportion of patients achieving resolution of an OFF to an ON state within 60 minutes after study drug is administered in the clinic, maintaining the ON state at 60 minutes after study drug administration (per the examiner's subjective assessment).
- Patient-reported total daily OFF time, total daily ON time without dyskinesia, total daily ON time with non-troublesome dyskinesia, and total daily ON time with troublesome dyskinesia, assessed by the patient and recorded in the patient diary.
- Change from baseline visit in the 39-Item Parkinson's Disease Questionnaire (PDQ-39).

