If a patient in the CVT-301 treatment group develops significant tolerability concerns that in the opinion of the investigator are of a severity that should necessitate a reduction in dose, including, but not limited to the exacerbation or worsening of troublesome dyskinesia, other problematic dopaminergic symptoms, or other tolerability concerns, a dose reduction from 2 capsules (50 mg LD FPD) to 1 capsule (25 mg LD FPD) per treated episode may be permitted. The medical monitor should be contacted, and the investigator should use his/her clinical judgment to determine whether an additional visit is required and what assessments should be performed (e.g., physical examination, spirometry, etc.). The patient should continue to use 1 capsule (25 mg LD FPD) per treated episode for a period of at least 1 week. If the investigator determines that the tolerability issue has adequately resolved and that the patient has tolerated this dose for at least 1 week, the patient may at that point either resume taking the original dose (2 capsules [50 mg LD FPD] per treated episode) or come into the clinic for an unscheduled visit to receive a reduced-dose study drug kit (35 mg LD FPD). Clinical staff will call the patient 1 to 2 days after the dose escalation to see if the patient has any questions or concerns. If a patient who has escalated back to the full dose (50 mg LD FPD per treated episode) has another tolerability concern that in the opinion of the investigator is of a severity that should necessitate a second reduction in dose, an unscheduled visit will be required and a reduced-dose study drug kit (35 mg LD FPD per treated episode) will be provided. He/she will remain on the reduced dose (35 mg LD FPD) for the remainder of the study; he/she will not be eligible for any additional up-titration in dose.

Safety data will be reviewed by an independent Data Safety Monitoring Board (DSMB) that will include relevant medical experts (including a neurologist and pulmonologist), an independent statistician, and additional representatives (as will be defined in the DSMB Charter). Safety data, including but not limited to AEs, spirometry, vital signs, and ECG data will be reviewed. The safety review will be documented in a DSMB Charter prior to the start of the study. In the event that potential safety issues are identified, the committee may recommend modification of the study design or study termination, which will be communicated promptly with investigators,

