- Distribute study drug kits to patients. Instruct patients to collect used empty capsules and return them at the next visit along with the PD Diary, Inhaled Dosing Log, and other study supplies.
- Re-train patients on the proper use of the inhaler with sham capsules, including a review of the IFU.

Study Drug Dosing

Immediately pre-dose, perform a spirometry assessment (record the patient's ON/OFF state on the spirometry source record). Under clinic staff supervision, preferably between 2 and 5 hours after receiving their standard dose of PD medication (in the OFF state), patients will prepare and self-administer their first dose of study drug from the study drug kits provided (i.e., 2 capsule inhalations of CVT-301). Patients will be permitted sips of water between capsule inhalations as needed. The dosing time is defined to be when the patient's OFF state is recognized by both the patient and investigator to be at a level similar to the investigator-confirmed severity experienced at SV1 and preferably between 2 and 5 hours after their prior oral PD medication.

Note: Instructions for how to properly use the CVT-301 system are outlined in the Instructions for Use document that is included with every CVT-301 study kit. Refer to [Appendix 21](#) for additional system information.

Post-dose (10 – 60 minutes)

The following post-dose safety evaluations will be performed:

- Record vital signs (standard and orthostatic BP and HR) at 20 and 60 minutes post-dose.
- Record RR at 10, 20, 30, and 60 minutes post-dose.
- Monitor for AEs throughout the visit.

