Upon completion of the 60-minute observations, resumption of normal medications is permitted for the remainder of the day (the patient may use the inhaled study drug 4 more times at home after he/she leaves the clinic on that day if needed for OFF episodes). The next visit will be scheduled. Clinic staff will arrange to speak with patients by telephone 1 to 3 days after TV/OV1 to monitor for AEs and to address any potential concerns or challenges with the inhaler systems or Inhaled Dosing Log. Additionally, clinic staff will arrange to speak with patients by telephone 2 weeks (\pm 3 days) before each visit for TV2, TV3, TV4, TV5, and TV6 to address any concerns or challenges with the inhaler systems, PD Diary, or Inhaled Dosing Log, to monitor for any AEs, to confirm the DLco assessment has been done/scheduled (prior to TV3, TV4, TV5, and TV6), to confirm the next study visit, to ask the patients how many empty study drug kits will be returned at the next visit, and also to remind patients of the study procedures

required prior to the next scheduled study visit (including completion of the PD Diary and Inhaled Dosing Log).

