11.1.12. Other Safety Assessments

11.1.12.1. UPDRS Part 4 (CVT-301 Treatment Group) and Examiner-Rated Dyskinesia

The UPDRS Part 4 is an assessment of potential complications of PD therapies. Questions 32-35 (related to dyskinesias) and 36-39 (related to clinical fluctuations) only will be completed for the CVT-301 patients as indicated in the time and events tables in [Appendix 2](#) through [Appendix 15](#).

Additionally, during the post-dosing follow-up period at TV/OV2, TV/OV3, TV/OV4, TV/OV5, and TV/OV6, observe the patient for the appearance of dyskinesia, and note in the eCRF if the patient experiences dyskinesia within the 60-minute post-dose period. If applicable, record the maximum severity of any dyskinesia during the 60-minute post-dose period. The examiner will also note if the patient converts to the ON state during the 60-minute post-dose period and if so, whether the patient is still in the ON state at 60 minutes post-dose.

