APPENDIX 6: TIME AND EVENTS TABLE—TREATMENT VISIT 2 (TV2) (1 MONTH [4 WEEKS ±5 DAYS] AFTER TV1)

Procedures	Arrival	Pre-dose	Time 0 (Dosing) ¹	10 min Post-dose	20 min Post-dose	30 min Post-dose	60 min Post-dose	End of TV2	Post-TV2 Telephone Contact
Collect, review, sign, and date PD Diary and Inhaled Dosing Log	X								
Collect empty capsules, inhalers, and unused supplies	X								
Record any changes in usual PD medication dose/regimen	X								
Record time of patient's prior usual PD medication dose	X								
Record any changes in concomitant medications	X								
Physical examination (brief)	X								
Vital signs (standard BP, HR, and RR and orthostatic BP and HR)		X ³							
Spirometry (preferably in ON state)	X								
C-SSRS	X								
Distribute study drug kits	X								
Review inhaler training	X								
Distribute PD Diary and Inhaled Dosing Log and review instructions for completion	X ⁴								
UPDRS Part 3		X ⁵		X	X	X	X		
Self-administration of study drug (in OFF state)			X ¹						
Monitor for dyskinesia and ON/OFF states						X			
Monitor for AEs					X				
Schedule next visit								X	
Schedule DLco visit at pulmonary site (14±3 days before next visit) ²								X	
Post-TV2 telephone contact: call patient 2 weeks (± 3 days) before TV3									X

¹Dosing of study medication occurs preferably between 2 and 5 hours after patient has taken normal morning dose of PD medication and after all pre-dose assessments are complete.

²DLco is to be performed in a dedicated pulmonary facility and includes slow vital capacity maneuver, DLco, and spirometry. Preferably in the ON state.

³Assessment can be done at any point after arrival but must be completed before dosing.

⁴The PD Diary is to be completed for the 3 consecutive days prior to TV3; the Inhaled Dosing Log is to be completed daily through TV6.

⁵Confirm patient is in the OFF state prior to pre-dose UPDRS Part 3 assessment.

APPENDIX 7: TIME AND EVENTS TABLE—OBSERVATIONAL VISIT 2 (OV2) (1 MONTH [4 WEEKS ±5 DAYS] AFTER OV1)

Procedures	Assess in Either ON or OFF State Unless Otherwise Noted	End of OV2	Post- OV2 Telephone Contact
Record any changes in usual PD medication dose/regimen	X		
Record any changes in concomitant medications	X		
Physical examination (brief)	X		
Vital signs (standard BP, HR, and RR and orthostatic BP and HR)	X		
Spirometry (preferably in ON state)	X (ON)		
C-SSRS	X		
Monitor for AEs	X		
Schedule next visit		X	

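### Examiner-rated dyskinesia, a secondary objective, is not rated after the first supervised in-study dose at TV1, so there is no first-dose rating and some early leavers and dose reducers may lack a full-dose rating

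*Protocol*

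**What the plan says.** The secondary objective in Section 6 reads: "To characterize the occurrence and severity of examiner-rated dyskinesia following treatment of patients experiencing an OFF episode in the clinic over a 12-month period". It names no visit as excluded, and the Synopsis repeats the measure among its safety criteria for evaluation.

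TV1 fits that description. Under Section 10.3.2.1, in the OFF state and under supervision, "patients will prepare and self-administer their first dose of study drug from the study drug kits provided", namely two capsules. Section 10.3.2.1 then introduces the post-dose period with "The following post-dose safety evaluations will be performed" and lists three items: BP and HR at 20 and 60 minutes, respiratory rate ("Record RR at 10, 20, 30, and 60 minutes post-dose") and adverse events. The length of observation is plain from what follows: "Upon completion of the 60-minute observations, resumption of normal medications is permitted for the remainder of the day".

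No examiner rating of dyskinesia or of conversion to ON appears in that list or in Appendix 4, the TV1 schedule. Section 11.1.12.1 assigns the rating to later visits: "during the post-dosing follow-up period at TV/OV2, TV/OV3, TV/OV4, TV/OV5, and TV/OV6, observe the patient for the appearance of dyskinesia". The row "Monitor for dyskinesia and ON/OFF states" first appears in Appendix 6, for TV2, which falls 4 weeks ± 5 days after TV1.

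Section 7 gives the grounds on which the dose may be reduced, "including, but not limited to the exacerbation or worsening of troublesome dyskinesia".

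**The concern.** The TV1 dose is the one in-study dose that every CVT-301 patient in the safety population takes, at one dose level, before any in-study reduction or drop-out. It is also the only supervised dose without a value for this endpoint.

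By TV2 the patient may have treated up to five OFF episodes a day at home for about four weeks. Background PD medication may have been modified and the study dose may have been reduced. The TV2 rating therefore mixes initial response, adaptation and dose change, and nothing earlier exists against which to read it. Conversion to ON after the first dose, an exploratory measure recorded in the same row, is missing for the same reason.

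The second issue is selection. The patients most likely to reduce or leave early because of dyskinesia are those the objective most needs to describe.

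**Working it through.** The protocol states no figure on this point, so there is nothing to reproduce. The check is a comparison of sections, followed by one calculation for scale.

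**1. TV1 against TV2**

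| | TV1 (10.3.2.1, App. 4) | TV2 (10.3.4.1, App. 6) |
|---|---|---|
| Supervised dose in OFF state | yes | yes |
| 60-minute post-dose observation | yes | yes |
| Adverse events monitored | yes | yes |
| Dyskinesia occurrence and maximum severity | no | yes |
| ON conversion, and ON at 60 minutes | no | yes |

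Both visits define the dosing time in the same way, by an OFF state similar to that seen at SV1. The gap is in what is recorded, not in whether the patient is dosed and watched.

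**2. Whether other data supply the rating**
- UPDRS Part 4 is completed on arrival at TV1, before dosing (Appendix 4).
- The PD Diary covers the three days before a visit, at home, and is rated by the patient.
- Adverse events are signs or symptoms that emerge or worsen (Section 11.1.8), graded in Table 3 by interference with everyday activities. Dyskinesia that is present but has not worsened need not be an adverse event, yet it would count as an occurrence under Section 11.1.12.1.

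None of these gives a systematic examiner record of occurrence and maximum severity over 60 minutes.

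**3. Who may lack a full-dose rating**
- Leavers before TV2: Sections 10.3.8.1 and 10.3.9 and Appendix 14 schedule the TV6 assessments at withdrawal, omitting only the pre-visit DLco. These include a supervised dose and the dyskinesia rating. Section 8.3 makes the visit a best effort. The leavers without a full-dose rating are those who do not attend, do not dose there, or dose at a reduced level.
- Reducers before TV2: Sections 7 and 10.3 let a patient go back to 50 mg after at least one week on one capsule, or move to the 35 mg kit. Those without a full-dose rating are the ones who do not return to 50 mg.

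**4. Scale of early leaving**

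Inputs: 250 CVT-301 patients and about 25% drop-out (Section 12.1). The protocol gives no month-1 rate, so a constant hazard over 364 days is assumed.

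Proportion leaving by day t = 1 − 0.75^(t/364)
- t = 28 (week 4): 1 − 0.75^(28/364) = 2.2%; 250 × 0.0219 = 5.5 patients
- t = 33 (week 4 plus 5 days): 1 − 0.75^(33/364) = 2.6%; 250 × 0.0257 = 6.4 patients

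That is about 5 to 6 of 250. As a front-loaded alternative, if half of all drop-out came before TV2, 0.5 × 25% = 12.5%, or about 31 of 250. Each count is an upper bound on unrated leavers for its pattern, because every leaver is scheduled for a rating at withdrawal. Reductions before TV2 cannot be sized, since the protocol gives no rate for them.

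**The case against.** The strongest defence is that nothing here contradicts itself. Sections 10.3.2.1 and 11.1.12.1 and Appendix 4 agree with one another. The dyskinesia and ON ratings belong with the post-dose UPDRS Part 3 assessments, a battery that starts at TV2. The objective is to characterise dyskinesia over 12 months, and five rated visits do that. A first-dose value is taken on drug and is not a baseline; the change-from-baseline dyskinesia objective is assigned to UPDRS Part 4, which is collected at TV1. Adverse events are monitored at TV1 and by telephone 1 to 3 days later and again 2 weeks before TV2, and they are graded mild, moderate or severe. All of this stands. The point is a gap in coverage, not an inconsistency, and TV1 is not blind to dyskinesia.

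Two stronger readings are tempting, and the protocol does not support either.
- A reader might infer that patients who leave or reduce before month 1 can never contribute a full-dose rating. The Early Withdrawal Visit includes a supervised dose with the rating, and a first reduction can be reversed after a week.
- A reader might infer a large downward bias at TV2. For example, if 25 of 250 (10%) had dyskinesia at the first dose and 8 to 12 of them left unrated, TV2 would show 17/242 = 7.0% to 13/238 = 5.5%. That needs more leavers for dyskinesia alone than the 5 to 6 from all causes under a constant hazard, with none of them rated at withdrawal. Front-loaded drop-out could raise the count, but the protocol gives no basis for assuming it.

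The defence does not show that any TV1 data replace the examiner rating, and the protocol gives no reason for leaving it out.

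**Conclusion.** The point holds as a low-cost improvement to the schedule. It is certain from the text that no examiner dyskinesia or ON rating is planned after the TV1 dose, so the secondary objective has no first-dose data and its first value comes about four weeks into treatment.

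The effect on selection is possible but unquantified. It is confined to the two groups identified in the working, and it may be informative because dyskinesia is a named trigger for reducing the dose. The figure of about 5 to 6 of 250 rests on the protocol's 25% drop-out and on an assumed constant hazard. It bounds unrated leavers under that pattern and says nothing about reducers.

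For patients carried over from CVT-301-002 or CVT-301-003, TV1 is the first dose in this study but not necessarily their first exposure. For them the gain is an early rating at the starting dose, not a first-exposure rating.

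**What to change.** Add the existing row "Monitor for dyskinesia and ON/OFF states" (occurrence and maximum severity of dyskinesia, conversion to ON, still ON at 60 minutes) to the 60-minute post-dose period of TV1, in both Appendix 4 and Section 10.3.2.1. Extend the visit list in Section 11.1.12.1 to run from TV1 through TV6. Summarise the ratings by visit and by the dose taken at that visit, so that full-dose and reduced-dose ratings are not pooled without distinction.

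The cost is one existing eCRF form completed at one more visit, within an observation period that is already staffed. It adds no visit or observation time, and dosing and patient management do not change.

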11.1.12.2. Columbia-Suicidality Severity Rating Scale

The C-SSRS is a measure of suicidal ideation and behavior. The rating scale has 4 general categories: suicidal ideation, intensity of ideation, suicidal behavior, and actual attempts. An initial baseline version will be given at TV/OV1, and a “since last visit” version will be given at all treatment visits to detect any emergence of suicidal ideation or behavior. The clinic staff should address any emerging neuropsychiatric needs in the event that the C-SSRS indicates active suicidal ideation.

11.1.12.3. Epworth Sleepiness Scale

The Epworth Sleepiness Scale is used to determine the level of daytime sleepiness. There are 8 situations listed (e.g., sitting and reading, watching television) for which patients rate their likelihood of dozing or sleeping (0=would never doze or sleep, 1=slight chance of dozing or sleeping, 2=moderate chance of dozing or sleeping, and 3=high chance of dozing or sleeping). A score of 10 or more is considered sleepy, and a score of 18 or more is very sleepy. The baseline assessment will be completed at TV/OV1 of this study. As described in the time and events tables in [Appendix 2](#) through [Appendix 15](#), additional assessments will be completed at TV/OV4 and TV/OV6.

11.1.12.4. Questionnaire for Impulsive-Compulsive Disorders in Parkinson’s Disease

The QUIP is an instrument used to measure the extent of impulsive and compulsive behaviors in PD patients. The QUIP has 3 sections: Section 1 assesses gambling, sexual, buying, and eating disorders; Section 2 assesses other compulsive behaviors (punding, hobbyism, and walkabout); and Section 3 assesses compulsive medication use. The baseline assessment will be completed at TV/OV1 of this study. As described in the time and events tables in [Appendix 2](#) through [Appendix 15](#), additional assessments will be completed at TV/OV4 and TV/OV6.

11.2. Exploratory Efficacy Assessments

Exploratory efficacy will be evaluated primarily for the CVT-301-treated patients. Exploratory efficacy will be evaluated from both in-clinic, at-home assessments, and patient-reported assessments as outlined by the criteria below. A limited number of patient-reported assessments identified in the subsections below (i.e., the PDQ-39, UPDRS Part 2, and S&E ADL) will also be performed in the observational cohort.

In-Clinic Criteria:

- UPDRS Part 3 motor score
- Occurrence of an ON state during the 60-minute post-dose period and if an ON state occurs during the 60-minute post-dose, whether or not the patient is still in the ON state at 60 minutes post-dose

At-Home Criteria and/or Patient-Reported Assessments:

- Total daily OFF time at home, total daily ON time without dyskinesia, total daily ON time with non-troublesome dyskinesia, and total daily ON time with troublesome dyskinesia, based on the PD Diary.
- PDQ-39
- PGI-C
- S&E ADL
- UPDRS Part 2

11.2.1. Assessment of ON and OFF States and Dyskinesia (CVT-301 Treatment Group)

An “OFF state” is defined as the time when medication is not providing benefit with respect to mobility, slowness, and stiffness. OFF episodes may be heralded by non-motor symptoms (e.g., pain, anxiety) prior to the appearance of motor symptoms.

An “ON state” is defined as the time when medication is providing benefit with respect to mobility, slowness, and stiffness, and may or may not be providing complete alleviation of all PD symptoms.

For recording motor state in the PD Diary, when patients are in an ON state, the presence and extent of dyskinesia (involuntary twisting, turning movements that are an effect of medication) will also be noted:

- ON with no dyskinesia
- ON with non-troublesome dyskinesia (ON with dyskinesia that does not interfere with function or cause meaningful discomfort)
- ON with troublesome dyskinesia (ON with dyskinesia that interferes with function or causes meaningful discomfort)

These ON and OFF definitions are to be used in training the patients to recognize and record their ON and OFF states. Patients will record their ON and OFF states in their diaries at home.

